10.11. Interim Analysis

After the first cohort completes the 6 month scans, an interim analysis will be conducted. If less than 20% of the patients have in-brain distant failure, then the next cohort will begin enrollment. If 20% or more of the patients have in-brain distant failure, then the study will stop.

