2.1. Primary Objective

Evaluate two de-escalated whole brain radiation dose levels (in the setting of simultaneous integrated boost to gross lesions) with respect to in-brain distant control for brain metastases, defined as an in-brain failure rate outside of the planning target volume at 6 months of < 20%.

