4.2. Exclusion Criteria

1. Previous radiation to the brain, including WBRT or brain radiosurgery.
2. Life expectancy < 6 months (as estimated per the current ds-GPA, see Appendix 1 for details).
3. For histologies not included in the ds-GPA publications or otherwise noted online at brainmetgpa.com, the PI will use either published or validated data, or the PI's best clinical judgment to determine the patient's expected survival.
4. Inability to comply with treatment per investigator discretion.
5. Inability to complete neurocognitive assessments per investigator discretion.

Of note, tumor lesion number is not an inclusion or exclusion criteria as we are using volume-based criteria instead.

5. **STUDY DESIGN**

This trial is a pilot, Phase 2, sequential two-cohort study designed to test two de-escalated WBRT dose levels and assess their ability to maintain acceptable in-brain distant control. The WBRT dose would decrease as we move forward in the study, both in terms of absolute value and EQD2 (i.e., equivalent dose in 2 Gray fractions, as determined by the linear quadratic radiobiological model). The absolute value of the SIB dose will change with each dose level because the number of fractions delivered will depend on the WBRT dose. As such, the SIB dose will be manipulated such that the EQD2 will remain essentially equivalent despite the difference in the number of fractions delivered. This design will ensure that the only variable is the change in WBRT dose.

The next phase of investigation would depend upon the outcome of this study. If we are able to demonstrate that both treatment levels in this study meet our primary endpoint, it would suggest that we have not yet found the lowest acceptable WBRT dose. As such, we would then consider a similar study in which we lower the WBRT dose further. If we do find the lowest acceptable WBRT dose, we envision that the next step would be an appropriately powered equivalency trial comparing that lowest acceptable WBRT dose with SIB vs standard WBRT alone vs standard radiosurgery alone. Outcomes in this trial would include standard efficacy outcomes, survival outcomes, and neurocognitive outcomes.

6. **PATIENT REGISTRATION**

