10.3. Criteria for Stopping Study

An interim analysis is planned when the final patient in Cohort A finishes their six month assessment. If 20% or more of the evaluable subjects have in-brain distant failure at the 6 month time point, then the study will stop.

Additionally, there will be an early stopping rule in place. Each patient will be evaluated at 6 months for in-brain distant failure. If 4 patients out of the first 10 patients within each cohort have in-brain distant failure at 6 months, then the expected percent of patients would be double of what is expected (40% vs the expected 20%). This finding will prompt a re-assessment of treatment efficacy to determine if the cohort should continue.

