10.5. Sample Size

A total sample size of 20 evaluable subjects per cohort was determined to balance the competing goals of assessing the primary objective while not exposing more subjects to an investigational decreased radiation procedure than is required. Historical data has shown that approximately 20% of subjects with standard radiation treatment show in-brain distant failure at 6 months. This trial is looking to see if decreased radiation will provide similar efficacy to the standard of care. There will be an interim analysis after the first cohort completes their 6 month scans. If less than 20% of the subjects have in-brain distant failure, then the second cohort will start.

With 20 evaluable subjects in a cohort, the 90% confidence interval around the proportion of subjects who are expected to have in-brain distant failure at 6 months would extend at most +/- 14.7%. Up to 25 subjects may be enrolled in each cohort. Although subjects who die before 6 months without confirmed in-brain distant failure would be replaced if possible, the following table will show the estimated confidence interval widths assuming the 20% proportion of subjects who may have in-brain distant failure at 6 months:

Number of Patients:	15	20	25
90% Confidence interval width:	17.0%	14.7%	13.2%

As stated in section 7.1.9, patients will not be considered evaluable if the sum total of radiotherapy interruptions exceeds 3 normally scheduled treatment days.

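### Does it undermine the plan that Cohort A stops the study at an observed 20%, the very rate the plan expects?

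*Combined protocol and SAP*

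**What the plan says.** Objective 2.1 sets the criterion for in-brain distant control, "defined as an in-brain failure rate outside of the planning target volume at 6 months of < 20" per cent. Section 10.11 applies it after the first cohort: "If 20% or more of the patients have in-brain distant failure, then the study will stop"; below 20%, Cohort B opens. Sections 10.3 and 10.5 state the same boundary.

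On the rationale, section 10.5 reports that "Historical data has shown that approximately 20% of subjects with standard radiation treatment show in-brain distant failure at 6 months" and adds: "This trial is looking to see if decreased radiation will provide similar efficacy to the standard of care". It plans 20 evaluable patients per cohort, with up to 25 enrolled, and justifies the number by the width of a 90% confidence interval. Section 10.3 also calls 20% the expected rate. It adds a rule within each cohort for four failures among the first ten patients: "This finding will prompt a re-assessment of treatment efficacy to determine if the cohort should continue".

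Section 10.8 reports the number of failures by cohort with an exact binomial 95% interval. Section 5 (Study Design) says what would follow if the investigators can "demonstrate that both treatment levels in this study meet our primary endpoint", namely that a further dose reduction would be considered. If the lowest acceptable dose is found, "the next step would be an appropriately powered equivalency trial".

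**The concern.** A trial that hopes to match a standard with about 20% failures appears to penalise itself for doing so. With 20 evaluable patients, 4 failures is both the expected count and the smallest count that ends the study. A dose level performing exactly like the standard would therefore stop the trial more often than not.

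The plan gives no go or stop probabilities for a binding rule and does not say what a stop after Cohort A would mean. With so few patients almost any stop is compatible with a true 20%, and almost any go is compatible with a rate well above it. The risk would be a report that Cohort A had failed, or that a rate below 20% had been shown, when the data support neither. The next study would then rest on that reading. The four-of-ten rule also seems to leave continuation open when, at 20 evaluable patients, the Cohort A outcome is already settled.

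**Working it through.** **Inputs.** From 10.5: n = 20 evaluable, historical rate 20%, interval widths tabulated at n = 15, 20 and 25. From 10.3 and 10.11: stop if the observed rate is 20% or more. From 10.8: exact binomial 95% interval.

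**The plan's own figure.** The 90% half-width is 1.645 × √(0.2 × 0.8 / n). This gives 16.99, 14.71 and 13.16 points at n = 15, 20 and 25, matching the stated 17.0, 14.7 and 13.2.

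**Stop probability at n = 20.** 4/20 = 20% stops and 3/20 = 15% continues, so P(stop) = 1 − P(X ≤ 3), with X binomial(20, p). At p = 0.20, P(X ≤ 3) = 0.0115 + 0.0576 + 0.1369 + 0.2054 = 0.411, so P(stop) = 0.589.

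| True rate | P(go) | P(stop) |
|---|---|---|
| 10% | 0.867 | 0.133 |
| 15% | 0.648 | 0.352 |
| 20% | 0.411 | 0.589 |
| 30% | 0.107 | 0.893 |
| 40% | 0.016 | 0.984 |

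**Dependence on n.** At a true 20%, P(stop) is 60.2% at n = 15, 40.2% at 16, 45.1% at 17, 49.9% at 18, 54.5% at 19, 58.9% at 20, 41.4% at 21, 45.7% at 22, 49.9% at 23, 54.0% at 24 and 57.9% at 25. It is below one half at six of these eleven sizes. The jumps come from rounding: 4/21 = 19.0% continues.

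**What the planned interval shows.** Exact 95% limits at n = 20:

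| Failures | Decision | Interval |
|---|---|---|
| 0 | go | 0 to 16.8% |
| 1 | go | 0.1 to 24.9% |
| 3 | go | 3.2 to 37.9% |
| 4 | stop | 5.7 to 43.7% |
| 8 | stop | 19.1 to 63.9% |
| 9 | stop | 23.1 to 68.5% |

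Every count from 1 to 8 includes 20%. At a true 20%, P(4 ≤ X ≤ 8) = 0.579 and P(X ≥ 9) = 0.010, so nearly all stops are of this kind.

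**Moving the boundary.** If exactly 20% counted as a go, P(go) at a true 20% would rise from 0.411 to 0.411 + 0.218 = 0.629. At a true 30% it would rise from 0.107 to 0.238.

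**Four of the first ten.** With 20 evaluable patients, four failures already give at least 4/20 = 20%. Cohort A could then continue to Cohort B only with 21 or more evaluable patients and no further failure (4/21 = 19.0%). At a true 20%, four or more failures among ten has probability 0.121.

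**The case for a change.** The best case for a change is that a binding rule deserves stated operating characteristics, fixed before the count is known. Section 5 speaks of demonstrating that the endpoint is met, and only 0/20 would put the planned interval wholly below 20%. An interpretation written after the interim would not be prespecified. All of this is arithmetically sound, and a short paragraph would be good practice.

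It does not, however, point to anything the trial would do differently. The rule, the objective, the sample size and the analysis would all stay as they are. Equality is placed explicitly on the stop side in both 10.3 and 10.11, in line with 2.1, so the intent is already legible. Section 5 is also more guarded than the one verb suggests: meeting the endpoint would suggest that the lowest dose has not been reached, a further study would be considered, and comparative proof is left to a later powered trial.

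The four-of-ten rule gives no opposite instruction. It acts earlier, applies within each cohort and asks for a re-assessment, whereas the Cohort A rule decides on Cohort B. Whoever carries out the re-assessment can see that four failures already reach the boundary at 20 evaluable patients.

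**Conclusion.** No change is needed. The stop at 20% is a fair trade-off. The decision it governs is whether to expose patients to a lower whole-brain dose, and section 10.5 gives limiting that exposure as a reason for the sample size. The price is a 59% chance of stopping at a true 20% with exactly 20 evaluable patients. Shifting the boundary would cut that to 37%, but would more than double the chance of proceeding at a true 30%, from 11% to 24%. Neither choice is plainly better.

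The absent probabilities and the absent reading of a stop are details that analysts can supply from the stated rule and n. The exact interval required by 10.8 will show readers that 1 to 8 failures in 20 do not separate the rate from 20%. A stop should be read as a decision on the observed rate, and the plan nowhere claims more for it.

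The figures assume independent patients with a common true rate among those evaluable. They ignore deaths, replacement, exclusion for treatment interruptions and any closure after the ten-patient re-assessment.

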11. DATA FORMS AND SUBMISSION SCHEDULE

This study will utilize electronic Case Report Form completion in the OnCore® database for all measures. A calendar of events and required forms are available in OnCore®. The OnCore® database is a comprehensive, web-based, Clinical Trial Management System (CTMS) which utilizes an Oracle database. OnCore® was developed by Forte Research Systems, Inc. and is used by the IUSCCC Clinical Trials Office (CTO) and supported by the Indiana Clinical and Translational Sciences Institute (CTSI). OnCore® properly used is compliant with Title 21 CFR Part 11.

OnCore® provides users secure access with unique IDs/passwords and restricts access by assigned roles, from any location, to record, manage, and report on data associated with the operation and conduct of clinical trials.

All source documents are to remain in the patient's clinic file. All documents should be kept according to applicable federal guidelines. Clinical trial data in OnCore® are periodically monitored by the IU Simon Comprehensive Cancer Center Data Safety Monitoring Committee.

12. PATIENT CONSENT AND PEER JUDGMENT

The protocol and informed consent form for this study must be approved in writing by the appropriate Institutional Review Board (IRB) prior to any patient being registered on this study.

Changes to the protocol, as well as a change of principal investigator, must also be approved by the Board. Records of the Institutional Review Board review and approval of all documents pertaining to this study must be kept on file by the investigator (housed in the Radiation Oncology Clinical Trials Office) and are subject to inspection at any time during the study. Periodic status reports must be submitted to the Institutional Review Board at least yearly, as well as notification of completion of the study and a final report within 3 months of study completion or termination.

The study will be conducted in compliance with ICH guidelines and with all applicable federal (including 21 CFR parts 56 & 50), state or local laws.

13. DATA AND SAFETY MONITORING PLAN

Investigators will conduct continuous review of data and patient safety. **Monthly review meetings for moderate risk trials** are required and will include the principal investigator, clinical research specialist and/or research nurse (other members per principal investigator's discretion). **Monthly** meeting summaries should include review of data, the number of patients, significant toxicities as described in the protocol, and responses observed. Summaries will be submitted and reviewed monthly by the DSMC. Submit to [contact].

13.1. Study Auditing and Monitoring

All trials conducted at the IUSCCCare subject to auditing and/or monitoring. Reports will be reviewed by the full DSMC at the time of study review (Reference Risk Table in full DSMC Charter).

13.2. Early Study Closure

At any time during the conduct of the trial, if it is the opinion of the investigators that the risks (or benefits) to the patient warrant early closure of the study, this recommendation should be made in writing to the Data Safety Monitoring Committee. Alternatively, the DSMC may initiate suspension or early closure of the study based on its review of the investigator reports.

13.3. Reporting Guidelines

The DSMC has streamlined the reporting process by utilizing reports from OnCore®. This has allowed direct view of reports within the Clinical Trials Management System (CTMS); thus discontinuing paper reports. SAE reports are entered into OnCore® monthly and reviewed by the DSMC chair and/or coordinator monthly. Findings will be reported to the full DSMC at the time of study review.

13.4. Study Accrual Oversight

Accrual data will be entered into the IU Simon Comprehensive Cancer Center OnCore® system. The Protocol Progress Committee (PPC) reviews study accrual twice per year while the PPC coordinator reviews accrual quarterly.

13.5. Protocol Deviations

Protocol deviations are entered into OnCore® and reviewed by the DSMC chair and/or coordinator monthly. Findings will be reported to the full DSMC at the time of study review.

14. REPORTING ADVERSE EVENTS

14.1. Definitions of Adverse Events

14.1.1. Adverse Event (AE)

An **adverse event** is defined as untoward medical occurrence associated with the use of an intervention in humans, whether or not considered intervention related. An adverse event can be **ANY** unfavorable and unintended sign (e.g., an abnormal laboratory finding), symptom, or disease temporarily associated with the use of an intervention, whether or not considered related to the intervention (attribution of ‘unrelated’, ‘unlikely’, ‘possible’, ‘probable’, or ‘definite’). Adverse events will be graded according to current CTCAE criteria.

14.1.2. Serious Adverse Event (SAE)

A serious adverse event is any untoward medical occurrence resulting in one or more of the following:

- Results in death or **ANY** death occurring within 30 days of a biopsy procedure (even if it is not felt to be related).
- Is life-threatening (defined as an event in which the patient was at risk of death at the time of the event; it does not refer to an event which hypothetically might have caused death if it were more severe)
- Requires inpatient hospitalization \geq 24 hours or prolongation of existing hospitalization

NOTE: Hospitalizations that are not considered SAEs are:

- Hospitalization planned prior to biopsy procedure
- Hospitalization $<$ 24 hours in duration
- Hospitalization for elective treatment of a pre-existing condition unrelated to biopsy procedure.
- Results in persistent or significant disability/incapacity
- Is a congenital anomaly or birth defect
- Is an important medical event (defined as a medical event(s) that may not be immediately life-threatening or result in death or hospitalization but, based upon appropriate medical and scientific judgment, may jeopardize the patient or may require intervention (e.g., medical, surgical) to prevent one of the other serious outcomes listed in the definition above). Examples of such events include, but are not limited to, intensive treatment in an emergency room or at home for allergic bronchospasm; blood dyscrasias or convulsions not resulting in hospitalization; or the development of drug dependency or drug abuse.

14.1.3. Unanticipated Problems

Investigators are required to submit unanticipated problems to the Indiana University Simon Comprehensive Cancer Center (IUSCCC) Data Safety Monitoring Committee (DSMC) (see Section 11.2 below) concurrent with their submission of them to the IRB. Prompt reporting of unanticipated problems to the IRB is defined as within 5 days for on-site studies.

Unanticipated problems that will be reported promptly to the IRB include:

- Major protocol deviation/violation

- Change to the protocol taken without prior IRB review to eliminate apparent immediate hazard to a research subject (e.g. purposeful and for subject safety)
- Complaint of a subject that indicates unexpected risks, or complaint that cannot be resolved by the research team
- Publication in the literature, safety monitoring report, interim result or other finding that indicates an unexpected change to the risks or potential benefits of the research, in terms of severity or frequency
- Investigator- or sponsor-initiated suspension or hold
- Serious or continuing non-compliance
- Adverse events (see Section 14.2 below)

14.1.4. Determining Attribution to the Intervention(s)

Attribution is an assessment of the relationship between the AE and the medical intervention. CTCAE v5.0 attribution categories will be used. CTCAE does not define an AE as necessarily “*caused by a therapeutic intervention*”. After naming and grading the event, the clinical investigator must assign an attribution to the AE using the attribution categories in Table 14-1 below.

Table 14-1. CTCAE Attribution Categories

Relationship	Attribution	Description
Unrelated to investigational intervention	Unrelated	The AE is clearly NOT related
	Unlikely	The AE is doubtfully related
Related to investigational intervention	Possible	The AE may be related
	Probable	The AE is likely related
	Definite	The AE is clearly related

14.2. Adverse Event (AE) and Serious Adverse Event (SAE) Reporting

Adverse events (AEs) will be recorded from the time of registration through 12 months after treatment (i.e., WBRT-SIB) regardless of whether or not the event(s) are considered related to the study procedure. All AEs considered related to study procedures will be followed until resolution, return to baseline, or deemed clinically insignificant, even if this occurs post-trial. Any death occurring within 30 days after the last study procedure must be reported as an SAE regardless of attribution.

14.2.1. Reporting to the IRB

Unanticipated problems involving risks to subjects or others will be reported **promptly** to the IRB if they:

- are unexpected;
- are related or possibly related to participation in the research; and
- suggest that the research places subjects or others at a greater risk of harm than was previously known or recognized.

If the serious adverse event does not meet all three (3) criteria listed above, the event does not have to be promptly reported to the Indiana University IRB. However, it should be reported at the time of continuing review.

Prompt reporting of unanticipated problems to the IRB is defined as within 5 days from becoming aware of the event.

14.2.2. Reporting to the IUSCCC Data Safety Monitoring Committee

Regardless of study sponsorship, the study team must enter all initial and follow-up SAE, expedited, and noncompliance reports into OnCore® for review by the DSMC chair and/or coordinator. Expedited reports may include IRB Prompt Report Forms and additional SAE forms as required by the sponsor. When follow-up information is received, a follow-up report should also be created in OnCore®. This DSMC reporting requirement is **in addition to any other** regulatory bodies to be notified (i.e. IRB, FDA, pharmaceutical company, etc.). The DSMC chair and/or coordinator will review all SAE, expedited, and noncompliance reports monthly and findings will be reported to the full DSMC quarterly.

16. APPENDICES

16.1. Appendix 1. Disease-Specific Graded Prognostic Assessment for Brain Metastases (ds-GPA)

Table 16-1. Disease Specific Graded Prognostic Assessment Criteria for Brain Metastases[8-11, 13]

Variable	Points						
	0	0.5	1	1.5	2	3	4
NSCLC							
Age, y	≥ 70	< 70	-	-	-	-	-
KPS	< 70	80	90 - 100	-	-	-	-
# of cranial metastases	> 4	1 - 4	-	-	-	-	-
Extracranial metastases	Present	-	Absent	-	-	-	-
Gene status (adenocarcinoma only)	EGFR neg/unk and ALK neg/unk	-	EGFR pos or ALK pos	-	-	-	-
SCLC							
Age, y	> 60	50 - 60	< 50	-	-	-	-
KPS	< 70	70 - 80	90 - 100	-	-	-	-
# of cranial metastases	> 3	2 - 3	1	-	-	-	-
Extracranial metastases	Present	-	Absent	-	-	-	-
Breast							
KPS	≤ 50	60	70-80	90 – 100	-	-	-
Histologic subtype	Basal	-	LumA	Her2	LumB	-	-
Age	≥ 60	< 60	-	-	-	-	-
Renal Melanoma							
KPS	< 70	-	70 - 80	-	90 - 100	-	-
# of cranial metastases	> 3	-	2 - 3	-	1	-	-
GI							
KPS	< 70	-	70	-	80	90	100

Notes: neg = negative; unk = unknown; pos = positive; basal = triple-negative; LumA = luminal A = ER/PR+ her2-; Her2 = ER/PR- her2+; LumB = luminal B = triple-positive.

Table 16-2. Median Overall Survival (months) per ds-GPA Score[10, 13]

GPA Score	NSCLC		SCLC	Melanoma	Renal cell	Breast	GI
	Adenocarcinoma	Nonadenocarcinoma					
0.0 - 1.0	6.9	5.3	3.0	3.4	3.3	3.4	3.1
1.5 - 2.0	13.7	9.8	5.5	4.7	7.3	7.7	4.4
2.5 - 3.0	26.5	12.8	9.4	8.8	11.3	15.1	6.9
3.5 - 4.0	46.8	-	14.8	13.2	14.8	25.3	13.5
Overall	15.2	9.2	4.9	6.7	9.6	13.8	5.4

Please refer to <http://www.brainmetgpa.com/> for the most up-to-date web-based version of this data that streamlines the scoring and assessment process for each patient. The table reproduced above was current at protocol inception, but the most up-to-date web-based version at time of registration should be used for each patient.

